2.8.4.2 Vital signs

Vital sign measurements include sitting systolic and diastolic blood pressures, sitting pulse, body temperature, height and body weight. Three sitting measurements of blood pressure (SBP and DBP) and pulse will be taken at each vital sign assessment.

For post-baseline assessments, the blood pressure and pulse values will be the average of the non-missing values of the 3 measurements. Derivation of baselines for blood pressure and pulse are provided in [Section 2.1.1](#).

Height and body weight will be collected at screening visit only and will be summarized in the baseline characteristic summary only.

Change from baseline to EOS visit in vital sign measurements will be summarized using descriptive summary statistics (mean, median, standard deviation, min, max). These descriptive summaries will be presented by vital sign parameter and treatment group. Change from baseline will only be summarized for patients with both baseline and post-baseline values and will be calculated as:

$$\text{change from baseline} = \text{post-baseline value} - \text{baseline value}$$

For vital signs data collected on Day 1, Day 7, Day 14, Week 4, and Week 8 protocol scheduled visit, pre and post-injection vital signs data including temperature, pulse rate and blood pressure are collected. Change from pre-injection to post-injection in these 3 parameters will be summarized by nominal visit.

The number and percentage of patients with clinically notable vital signs will be presented. For clinical notable vital signs values, refer to [Section 5.4](#).

All above summaries include only data up to and including safety cut off.

2.8.5 Suicidality ideation and behavior

The Columbia Suicide Severity Rating Scale (C-SSRS) questionnaire will be administered electronically (eC-SSRS), via an interactive voice response (IVR) system. However, as per internal Novartis guidelines, a CRF page ‘Supplemental Data for Suicidal Ideation and Behavior Categories’ is also used as an unplanned/unscheduled visit for those cases when the

subject did not conduct the phone interview because, e.g. the subject was hospitalized and unable to conduct the interview or the subject refused to conduct the interview/withdrew from the study and external information on suicidal ideation and behavior (SIB) is required. In such cases, SIB information will still be collected from external parties (spouse, caregiver, nurse, investigator, etc.) through means of this CRF page. Further, for deaths due to suicide, the site should fill out the Supplemental Data CRF (“completed suicide” tickbox) to ensure accurate reporting of such cases. When reporting the SIB data, data from both sources (IVR eC-SSRS and Supplemental CRF) will be used in a pooled manner and no distinction will be made between the two.

Table 2-8 Standard SIB events as categorized by C-SSRS

Category number	C-SSRS category
Suicidal Ideation	
1	Wish to be dead
2	Non-specific active suicidal thoughts
3	Active suicidal ideation with any methods (not plan) without intent to act
4	Active suicidal ideation with some intent to act, without specific plan
5	Active suicidal ideation with specific plan and intent
Suicidal behavior	
6	Preparatory acts or behavior
7	Aborted attempt
8	Interrupted attempt
9	Actual attempt
10	Completed suicide
Self-injurious behavior, without suicidal intent	
11	Non-suicidal self-injurious behavior

Definition of ‘all prior history’ and ‘recent history’

SIB will be collected once before randomization, either at screening or at baseline visits. SIB assessments obtained before the first dose of study drug will be defined by two components: *all prior history and recent history*.

All prior history will be defined as the SIB results obtained from the *lifetime* assessment, and *recent history* will be defined as the SIB results obtained from the *pre-defined period (i.e., past 6 months or 24 months)* assessment of the screening or baseline visit. If there are multiple assessments prior to first dose, the worst case value will be used for *All prior history*, and *recent history* respectively. Worst case is defined by answer ‘yes’ to the SIB category.

Data summaries

SIB data will be summarized for the Safety set. The number and percentage of subjects with suicidal ideation, suicidal behavior and self-injurious behavior without suicidal intent will be presented by analysis-period (recent history, all prior history and any time post-baseline) and treatment group. The following 14 events will be included in the summary table:

- Each of the 11 categories listed in [Table 2-8](#), separately
- Any suicidal ideation or behavior (a ‘yes’ answer to at least one of the 10 suicidal ideation and behavior questions in analysis-period of interest)
- Any suicidal ideation (answered ‘yes’ to at least one of the 5 suicidal ideation questions in analysis-period of interest)
- Any suicidal behavior (answered ‘yes’ to at least one of the 5 suicidal behavior questions in analysis-period of interest)

In addition, the number and percentage of subjects with the following post-baseline events will be presented ([Nilsson et al. 2013](#)):

Note: in these definitions, a category of 0 is assigned to a subject without suicidal ideation (i.e. a ‘no’ answer to all suicidal ideation categories)

- Worsening suicidal ideation compared to recent history: An increase in the maximum suicidal ideation category at any time post-baseline from the maximum suicidal ideation category during pre-treatment recent history.
- Worsening serious suicidal ideation compared to recent history: An increase in the maximum suicidal ideation category to 4 or 5 at any time post-baseline from not having serious suicidal ideation (categories of 0-3) during pre-treatment recent history.
- Emergence of serious suicidal ideation compared to recent history: A maximum suicidal ideation category of 4 or 5 at any time post-baseline from no suicidal ideation (category 0) during pre-treatment recent history.
- Improvement in suicidal ideation at last on-treatment measurement compared to recent history: A decrease in suicidal ideation score at last on-treatment measurement from pre-treatment recent history.
- Emergence of suicidal behavior compared to all prior history: The occurrence of suicidal behavior (Categories 6-10) at any time post-baseline from not having suicidal behavior (Categories 6-10) prior to treatment (includes “lifetime” and any other assessments prior to treatment taken prior to treatment).

For those analyses, each subject can only be counted once for each event. However, a subject can be counted in several different events.

Suicidal ideation and behavior data will be listed. Detailed answers to C-SSRS items will be listed separately for subjects with any suicidal ideation at any time post-baseline (i.e. a ‘yes’ answer to at least one of the five suicidal ideation questions at any time post-baseline) and for a subject with any suicidal behavior at any time post-baseline (i.e. a ‘yes’ answer to at least one of the five suicidal behavior questions at any time post-baseline).

2.8.6 Safety evaluation during the Safety follow-up

Safety data collected after last administration of study drug includes adverse events, vital signs, routine laboratory parameters, laboratory assessments to measure total IgG, total IgM, B-cell repletion, and eCSSRS. No safety cutoff date will be applied in the analyses defined in this section. As stated in [Section 2.1](#), the Week 12 Registration CSR will contain only partial data

collected from the Safety FU. A complete analysis of the post-treatment safety follow-up will be provided in the Final CSR when all patients have completed the Safety FU.

2.8.6.1 Analysis in the Week 12 registration CSR

In CSR, due to the small number of patients expected to have data and only partial data after study drug discontinuation, such data will only be included in respective listings as applicable.

2.8.6.2 Analysis in the Final CSR

The number and percentage of patients with at least one TEAEs that started after the date of last administration of study drug will be reported by SOC, preferred term, and treatment group. The subset of patients in SAF who had data reported after the date of last administration of study drug will be included in the analysis and the number of patients in this subset will be the denominator in calculating the percentage.

The vital signs data collected after study drug discontinuation will be summarized as summary statistics of the vital sign measures and of the change from baseline in the vital sign measures by treatment group for each visit-window after study drug discontinuation (as defined in [Section 2.1.2.1](#)). The analysis will be limited to the subset of patients in SAF who either completed the treatment period on study drug and do not enter the extension study or prematurely discontinued study treatment.

The B-cell counts and its change from baseline values will be summarized by treatment group for each visit-window after study drug discontinuation. The analysis will be limited to the subset of patients in SAF who had B-cell count data after the date of last administration of study drug and either completed the treatment period on study drug and do not enter the extension study or prematurely discontinued study treatment; the number of patients in this subset will be the denominator in calculating the percentage.

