				
Removed reference to protocol deviation ID INCL01 to prevent inappropriate exclusion of patients with this PD ID from analyses: At the time of writing of the SAP it was assumed that INCL01 would be assigned to PD “Informed consent obtained = 'No' or missing”, however, in the database no code was assigned to this deviation (and no patients affected), while INCL01 was in fact assigned to “Incorrect ICF procedure” as per Edit Check Specifications – which does not justify exclusion of patients from analysis. Impact: Change allows inclusion of data from two patients who consented, but were affected by incorrect ICF procedure in all analyses.
 
Document history: Correct date of amendment 2 to release date 18 Sep 2019 as provided on title page.

8- May- 2020	After DBL	Adapt plan for reporting of SFU patients to very low sample size	Addendum 2	
Section 2.1.2.1: Updated visit window definition for data after study drug discontinuation (replaced EOS date with Last dose date as starting point for visit window definitions).
 
Section 2.8.6.2: Clarify that only patients that did not roll over to the extension study or prematurely stopped treatment should be included in SFU analyses, to avoid contributions from patients not in SFU, who had unscheduled assessments shortly after the regular EOS/Week 12 visit.

Date	Time point	Reason for update	Outcome for update	Section and title impacted (Current)
				

Table of contents

Table of contents	7
List of abbreviations	9
Pharmacokinetic definitions and symbols	11
1 Introduction	12
1.1 Study design.....	12
1.2 Study objectives and endpoints	15
2 Statistical methods.....	15
2.1 Data analysis general information	15
2.1.1 General definitions	16
2.1.2 Visit windows.....	18
2.2 Analysis sets	20
2.2.1 Subgroup of interest	20
2.3 Patient disposition, demographics and other baseline characteristics	20
2.3.1 Patient disposition	20
2.3.2 Background and demographic characteristics.....	20
2.3.3 MS baseline disease characteristics	21
2.3.4 Medical history.....	21
2.4 Treatments (study treatment, rescue medication, concomitant therapies, compliance).....	21
2.4.1 Study treatment	21
2.4.2 Prior, concomitant and post therapies	22
2.5 Analysis of the primary objective.....	23
2.5.1 Primary endpoint.....	23
2.5.2 Statistical hypothesis, model, and method of analysis.....	24
2.5.3 Handling of missing values/censoring/discontinuations.....	25
2.5.4 Supportive analyses.....	25

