No clinically significant difference in ofatumumab exposure is expected between the two administration sites (abdomen vs thigh) (Xu et al 2010). Groups 3 and 4 will enable an assessment of the pharmacokinetics of ofatumumab injected to the thigh which can then be compared to abdominal administration using the PFS and AI, respectively. The aim of assessment of the injection site influence on ofatumumab pharmacokinetics is not to demonstrate bioequivalence but to enable an evaluation of the potential clinical significance of differences in pharmacokinetic parameters. Potentially, the absorption rate may vary between different injection sites for subcutaneous single dose administration of ofatumumab possibly resulting in different T_{max} and C_{max} values. However, under steady-state conditions and with the primary target being depletion of CD20-positive B-cells, the comparison of AUCs over the dosing period would be the most relevant parameter to evaluate. In order for patients to obtain a clinical benefit from participation in the study, continued treatment with ofatumumab will be offered to the eligible patients through enrollment into the umbrella open-label Phase 3 extension study (COMB157G2399). Patients waiting for open label extension study to open can continue to receive study drug. Patients should return every 12 weeks and complete assessments per assessment schedule.

Part 3 – Safety follow-up/Extension study

- The Safety FU period will be applicable for the following patients:
 - a. Patients who complete the Treatment period on study drug and do not enter the planned Extension study
 - b. Patients who prematurely discontinue study treatment
- All Safety FU visits must be scheduled relative to the EOS Visit.
- All patients will be followed for a total of at least 9 months after study drug discontinuation (by 9 months the vast majority of patients are expected to have repleted their circulating B-cells).

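### The safety follow-up AE table in SAP 2.8.6.2 admits patients who rolled over to the extension, unlike the vital-sign and B-cell tables in the same section

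*SAP*

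**What the plan says.** SAP 2.8.6.2 sets a population for each of three follow-up tables in the Final CSR.

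- **Adverse events.** The table counts patients with "at least one TEAEs that started after the date of last administration of study drug". Its base and denominator are "The subset of patients in SAF who had data reported after the date of last administration of study drug". No condition on extension entry is attached.
- **Vital signs.** The table is limited to safety-set patients "who either completed the treatment period on study drug and do not enter the extension study or prematurely discontinued study treatment".
- **B-cells.** The table requires a B-cell count after the last dose "and either completed the treatment period on study drug and do not enter the extension study or prematurely discontinued study treatment".

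SAP 1.1 says who belongs to the safety follow-up. One group is "Patients who complete the Treatment period on study drug and do not enter the planned Extension study"; the other is patients who stop study treatment early. On duration it says: "All patients will be followed for a total of at least 9 months after study drug discontinuation".

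The document history entry for Addendum 2 describes the change to 2.8.6.2 as clarifying that "only patients that did not roll over to the extension study or prematurely stopped treatment should be included in SFU analyses", and gives the reason: "to avoid contributions from patients not in SFU, who had unscheduled assessments shortly after the regular EOS/Week 12 visit". The same entry describes the follow-up sample as very low and gives no number.

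**The concern.** The AE paragraph selects patients by whether they have data after the last dose. The other two paragraphs select them by whether they left treatment. These are different groups of people.

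A patient who completes and moves to G2399 continues on ofatumumab. The sixth planned injection is at Week 12 (Protocol 9.3, SAP 2.4.1), so such a patient can have a stretch of time in this study after the last injection and before extension entry. Anything reported in that stretch satisfies the AE paragraph.

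A reader of the Final CSR would expect the follow-up AE table to describe patients who have stopped the drug, over a period of 9 months or more. As defined, it can combine them with patients who have not stopped and are seen only until they enter the extension. Its denominator would also differ from those of the neighbouring follow-up tables, with nothing in the SAP to explain the difference.

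**Working it through.** **Step 1: set the three definitions side by side (SAP 2.8.6.2).**

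| Table | Data after last dose required | Rollover patients excluded |
|---|---|---|
| AEs | yes | no |
| Vital signs | not stated as a condition | yes |
| B-cells | yes | yes |

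The B-cell paragraph imposes both conditions. Post-dose data alone was therefore not treated there as enough to identify a follow-up patient.

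**Step 2: look for a limit elsewhere.**

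- SAP 2.8.6, the parent section, adds no population limit and lifts the safety cutoff for these analyses.
- SAP Table 2-1 ends AE reporting in the Final CSR at 100 days after the last dose or at entry into G2399, whichever is earlier. If that stop still applies here, it shortens a rollover patient's window. It does not remove the patient from the numerator or the denominator.
- I found no other text that supplies the missing restriction.

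**Step 3: see how a rollover patient enters.**

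- Through an unscheduled laboratory or vital-sign assessment with no AE: the denominator rises by one and the numerator does not change. The percentage falls.
- Through an AE, which is itself reported data: numerator and denominator both rise by one. The percentage rises, unless it is already 100%.

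**Step 4: size.** The plan states no figure for this table, so there is nothing to reproduce. Let *s* be the true follow-up patients, *p* their share with a post-dose AE, *m* the rollover patients with any post-dose data, and *q* the share of those with a post-dose AE. Then

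percentage shown = (s·p + m·q) / (s + m).

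This is below *p* when q < p, equal when q = p, and above when q > p. The documents give none of the four quantities, so the values below are assumptions. Take s = 10 and p = 50%, that is, 5 patients with an AE. The restricted table shows 5/10 = 50%. With the present wording:

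| m | q = 0 | q = 10% | q = 100% |
|---|---|---|---|
| 5 | 5/15 = 33% | 5.5/15 = 37% | 10/15 = 67% |
| 20 | 5/30 = 17% | 7/30 = 23% | 25/30 = 83% |
| 140 | 5/150 = 3% | 19/150 = 13% | 145/150 = 97% |

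The last row is only an outer bound: the planned total of about 150 patients less the 10 assumed.

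Over a wider assumed range (s = 5 to 15, p = 30% to 50%, m = 5 to 50):

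- q = 0: from 1.5/55 = 2.7% to 7.5/20 = 37.5%
- q = 100%: from (4.5 + 5)/20 = 47.5% to (2.5 + 50)/55 = 95.5%

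These figures show that the result is sensitive and that its direction is open. They are not estimates for this trial.

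**The case against.** The strongest reply is that the AE paragraph does what it says: it tabulates events starting after the last dose among patients with data after the last dose. A separate AE population could be deliberate. The reason given in the document history concerns unscheduled assessments, which suits measurements summarised in visit windows (the first post-treatment window in SAP Table 2-6 opens on day 2), and AEs have no such windows. A difference between a change log and the current text is also not an error in itself. That last point is correct, and the finding does not rest on the log. The inconsistency lies within the current text of 2.8.6.2; the log only indicates intent, and it refers to follow-up analyses without excepting AEs. The SAP gives no reason for treating AEs differently.

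A second reply is that few patients may be involved. Protocol 3.6 presents the extension as a direct continuation, and Table 2-1 stops AE reporting at extension entry. This stands as a limit on size. Nor is the last dose always at Week 12: early discontinuers stop sooner, and patients waiting for the extension may go on receiving study drug.

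In the other direction, a reader might infer that follow-up AE rates are necessarily diluted, because rollover patients are likely to be observed only briefly. The documents do not support that. A rollover patient may be in the subset precisely because of an AE, and such a patient raises the percentage. Without the number of these patients and their AE share, neither direction nor size can be stated.

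**Conclusion.** The AE paragraph of SAP 2.8.6.2 is wrong as written. It places patients who are outside the safety follow-up, as SAP 1.1 defines it, into a safety follow-up table, and it does not match the other two tables in its own section. The percentages can be distorted either way.

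The conclusion assumes that the last administration means the last injection in this study. It also assumes that at least some rollover patients have data between that injection and extension entry. The Addendum 2 entry, dated after database lock, refers to post-Week 12 unscheduled assessments in patients outside the follow-up, which makes the second assumption reasonable.

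The consequence is minor. It is confined to one descriptive table in the Final CSR, with no test attached. The bioequivalence analysis and the main treatment-emergent AE tables are unaffected.

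**What to change.** In the AE paragraph of SAP 2.8.6.2, limit both numerator and denominator to safety-set patients who completed treatment and did not enter the extension, or who discontinued early. This is the restriction already written for vital signs and B-cells. If a different population is intended for AEs, the SAP should say so, give the reason, and footnote the table accordingly.

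The cost is one filter in one table. No AE information is lost: events in rollover patients before extension entry remain in the main treatment-emergent AE tables, subject to their usual cutoff, and in the listings.

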- The Safety FU period [Table 6-2](#) will be applicable for the following patients:
 - a. Patients who complete the Treatment period on study drug and do not enter the planned Extension study

- b. Patients who prematurely discontinue study treatment
- All Safety FU visits must be scheduled relative to the EOS Visit.
- All patients will be followed for a total of at least 9 months after study drug discontinuation (by 9 months the vast majority of patients are expected to have repleted their circulating B-cells, see IB).
- A longer than 9 months of post-treatment follow up in the Safety FU period will be required for patients who have not repleted their B-cells (ie B-cells not back to baseline value or to lower limit of normal (LLN) whichever comes first as determined by central lab) at 9 months. These patients will continue to be followed with 3-monthly assessments until their B-cell counts have repleted. Patients who have initiated therapy with another disease modifying/immunosuppressive therapy before the end of the 9-month follow up will not be monitored beyond 9 months.

[figure not shown]

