If the patient cannot attend any further study visit(s), the site staff should maintain regular telephone contact with the patient, or with a person pre-designated by the patient, unless the patient has withdrawn informed consent (see [Section 5.6.3](#)). This telephone contact should preferably be done according to the study visit schedule

The Investigator must also contact the IRT to register the patient's discontinuation from study treatment.

Note: Patients who prematurely discontinue study drug and complete their EOS visits will enter the Safety FU period ([Table 6-2](#)) for continued follow-up (See [Section 3.1](#), [Section 5.6.1](#)). The Investigator should consider the benefit/risk of initiation of alternative MS therapy in terms of the patient's clinical status, local regulations, treatment guidelines and local prescribing information.

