Table 6-2 Assessment schedule for Safety Follow-up period

Visit Week ¹ (relative to EOS)	+W12	+W24	+W36	Every 12 Weeks ²	End of Safety-FU ³
Visit Number	410	420	430	440/4XX	2999
Visit window (days)	±14	±14	±14	±14	
AEs	X	X	X	X	X
Concomitant Meds*	X	X	X	X	X
Vital Signs	X	X	X	X	X
eCSSRS	X	X	X	X	X
Urine pregnancy test ⁴	X	X	X	X	X
Contraception status	X	X	X	X	X
Sample for Total IgG, IgM	X	X	X	X	X
Routine Labs	X	X	X	X	X
Follow up Disposition					X

W=week.

1. Time measured from the EOS visit
2. As needed for the patients requiring [REDACTED] (Section 3.1)
3. If planned visit and End of Safety-FU occur at the same time only End of Safety-FU visit should be done. If patient is prematurely withdrawn from the Safety-FU period, the End of Safety-FU assessments should be done at the time of withdrawal
4. Female patients only: monthly urine home pregnancy testing will be conducted between clinic visits. The patient must contact the Investigator immediately in the case of a positive test for confirmatory testing at the Investigator's discretion

* including steroids for MS relapse and newly started disease modifying therapy as applicable

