A longer than 9 months of post-treatment follow up in the Safety FU period will be required for patients who have not repleted their B-cells (ie B-cells not back to baseline value or to lower limit of normal (LLN) whichever comes first as determined by central lab) at 9 months. These patients will continue to be followed with 3-monthly assessments until their B-cell counts have repleted. Patients who have initiated therapy with another disease modifying/immunosuppressive therapy before the end of the 9-month follow up will not be monitored beyond 9 months.

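### The readable SAP text for the post-discontinuation B-cell summary does not separate counts taken after a patient starts another B-cell-lowering therapy, so a switch could be read as slower recovery after ofatumumab

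*SAP*

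**What the plan says.** SAP 2.8.6.2 (Analysis in the Final CSR) plans a descriptive analysis: "The B-cell counts and its change from baseline values will be summarized by treatment group for each visit-window after study drug discontinuation". The population is "limited to the subset of patients in SAF who had B-cell count data after the date of last administration of study drug" and who either completed treatment without entering the extension study or stopped treatment early. The sentence ends with "the number of patients in this subset will be the denominator in calculating the percentage", but no numerator is given. SAP 2.8.6 adds: "No safety cutoff date will be applied in the analyses defined in this section".

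The protocol foresees a change of therapy in this group:

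- Section 5.6.2, in a note on patients who stop early: "The Investigator should consider the benefit/risk of initiation of alternative MS therapy".
- Section 5.6.2 also lists use of a prohibited treatment as a reason for permanent discontinuation. Table 5-1 names B-cell depleting antibodies among the prohibited treatments.
- Table 6-2 (Safety Follow-up schedule), footnote to concomitant medications: "including steroids for MS relapse and newly started disease modifying therapy as applicable".
- Section 3.1: "Patients who have initiated therapy with another disease modifying/immunosuppressive therapy before the end of the 9-month follow up" are not followed after 9 months. SAP 1.1 repeats this: such patients, if they start the therapy "before the end of the 9-month follow up will not be monitored beyond 9 months". Up to 9 months they remain in follow-up.

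**The concern.** SAP 2.8.6 names B-cell repletion as one of the things measured after the last dose. A count taken while a patient is on a new B-cell depleter does not measure repletion after ofatumumab. It mainly reflects the new drug. If such counts are pooled with counts from patients on no further therapy, the summary for that window is pulled down, and recovery after ofatumumab looks slower than it was.

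The group is small. The SAP document history gives a very low sample size as the reason for Addendum 2, and the results are then split by treatment group and visit window. In cells of that size one suppressed count can visibly move a mean. Addendum 2 had already narrowed the population of this section to keep out patients who were not really in safety follow-up. Counts after a switch raise a similar question of what the summary represents, and the readable text does not address it.

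**Working it through.** The documents give no sample size, repletion rate or switching rate for this summary, so there is no planned figure to reproduce. The check is a reading of the rules followed by an illustration.

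**1. Is there a handling rule elsewhere?** The 9-month provision in Protocol 3.1 and SAP 1.1 decides how long a patient is followed, not which counts are analysed. SAP 2.4.2.1 classifies and tabulates drugs started after discontinuation but does not link them to the B-cell summary. No readable sentence excludes, censors, flags or separates post-switch counts.

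**2. Which windows could be affected?** SAP Table 2-6 gives days 2–126, 127–210 and 211–294 after the last dose. Part of its title is redacted, so its use for B-cells is an assumption. At 30 days per month, 9 months is 9 × 30 = 270 days, inside the Week 36 window (211 ≤ 270 ≤ 294). Post-switch counts could therefore enter all three windows.

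**3. How many patients?** The planned 3% dropout allows for (124 − 120) + (26 − 24) = 6 patients over four arms. Completers who do not enter the extension add to this; their number is not given.

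**4. Effect on the planned output (illustration).** Let a cell hold n patients, k of them post-switch. Let m be the mean count that all would have without a switch, and c the mean count on the new drug.

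- Reported mean = [(n − k)m + kc] / n
- Relative fall = (k/n)(1 − c/m), which is k/n when c is near zero

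| n | Fall in the mean, k = 1, c ≈ 0 |
|---|---|
| 2 | 1/2 = 50% |
| 5 | 1/5 = 20% |
| 10 | 1/10 = 10% |
| 20 | 1/20 = 5% |

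**5. Effect on a repletion percentage, only if one is reported.** Let p be the true repleted share, and count each switcher as not repleted. The reported share is p(n − k)/n, a fall of pk/n. For k = 1 and p from 0.5 to 0.8, the fall is 25 to 40 percentage points at n = 2, 10 to 16 at n = 5, 5 to 8 at n = 10, and 2.5 to 4 at n = 20.

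The values of n, k, c and p are assumptions. None comes from the documents.

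**The case against.** The case against has five parts.

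- **Redaction.** Text is blacked out directly after the B-cell sentence in SAP 2.8.3.2, in the title of Table 2-6, and in a document-history entry about a corrected data cutoff. A handling rule could sit there. This stands as a limit: the point can be made only about the readable text.
- **No repletion outcome.** A reader might infer that a switch to a B-cell depleter will be reported as failure to replete after ofatumumab. The documents do not support that. The readable SAP plans counts and change from baseline. The criterion of return to baseline or the lower limit of normal only decides who is followed beyond 9 months, and the percentage has no numerator. This stands in full.
- **No evidence of frequency.** Neither document gives a switching rate. Section 5.6.2 asks investigators to weigh the benefit and risk of another therapy; it does not say that patients will switch. This also stands.
- **The information is available.** Post-discontinuation drugs are tabulated, B-cell data in follow-up are listed, and in a small group a reader can check individuals. This reduces the harm but leaves the summary table mixed.
- **All observed counts are a legitimate description, and dropping counts has its own cost.** Removing values after every disease-modifying therapy would be too broad. The mechanism here concerns only drugs that lower B-cells, and exclusion can select who remains. This shapes the fix.

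**Conclusion.** The gap is real but narrow. On the readable text, counts taken under a new B-cell-lowering therapy would be pooled with recovery after ofatumumab, although the switch is foreseen and recorded and these patients stay in follow-up to 9 months. If such a switch occurs, the counts are biased downwards and could be read as slower recovery.

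The size cannot be fixed from the documents. Under the stated assumptions, one switcher with a count near zero lowers a cell mean by 1/n; with no such switcher there is no effect. The conclusion also rests on the redacted B-cell text containing no handling rule.

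This is a descriptive safety summary. B-cell recovery is not among the endpoints in Protocol Table 2-1 or SAP Table 1-1, and the bioequivalence analysis is not affected. It ranks as a cheap improvement.

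**What to change.** In SAP 2.8.6.2:

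1. Base the B-cell recovery summary on counts before the start date of any new B-cell-depleting or other B-cell-lowering disease-modifying or immunosuppressive therapy. Use the start date already recorded, including a therapy begun before the last dose, which SAP 2.4.2.1 would class as concomitant. Specify in advance which therapies count as B-cell-lowering.
2. Show the all-values summary alongside, with the number of patients in each window for both.
3. Flag post-switch counts in the listing and name the therapy.
4. Define the numerator of the percentage, or delete the reference to it.

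The cost is SAP wording, one date comparison on data already collected, and one extra display. The downside is fewer values in the later windows and possible selection among the patients who remain; the side-by-side display makes both visible. If the redacted text already holds such a rule, a cross-reference from 2.8.6.2 covers items 1 to 3, as far as that rule goes.
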